4.6 EXPLORATORY ENDPOINTS

4.6.1 Infant Growth Velocity

Infant growth velocity will be assessed by recording the infant's weight (kg), height (cm) and head circumference (cm) at birth, and Months 2, 4, 6, 9, and 12. Analysis will be based on the SAFI and includes:

Actual values and change from baseline (defined as at birth) for weight,
 length/height, head circumference, and growth velocity (defined as the change

- from baseline divided by the number of months since baseline) will be summarized at each age time-point (birth, and Months 2, 4, 6, 9 and 12).
- The weight-for-age, length/height-for-age, and head circumference-for-age percentiles and change from baseline percentiles at each time-point will be summarized.
- The number and percentage of infants in the 3rd, 5th, 10th, 25th, 50th, and >50th percentile of the WHO growth charts will be presented for weight-forage, length/height-for-age, and head circumference-for-age percentiles at each age time point. The number and percentage of infants within 10th-90th percentile, and 3rd-97th percentile of the WHO growth charts will also be presented.
- Shift tables will be presented for each parameter to compare the change from infant's percentile at baseline (≤ 3rd, >3rd ≤5th, >5th ≤10th, >10th ≤25th, >25th -≤50th, >50th) to each age time-point (WHO 2006; WHO 2007; WHO 2017).
- Mean percentiles for weight-for age, length/height-for-age, and head circumference-for-age and corresponding 90% CIs will be plotted over time.
- Individual growth charts will be presented for each infant. This chart will present the weight, length/height, and head circumference-for-age for the infant over time, including reference lines for the 3rd, 25th, 50th, 75th, 90th and 97th percentiles for weight-for-age, length/height-for-age, and head circumference-for-age from WHO growth charts. Separate plots will be produced for each infant. Combined plots will also be produced for males and females separately, to show the trajectories of each infant on the same page.

All observed assessments will be included in the analysis; no imputation for missing assessments will be performed. Analyses will also be presented for the following subgroups:

 Type of feed: exclusive breast milk since birth to month 6 vs others (including complementary feeding [breastmilk + formula milk, in various proportions] and formula feeding [no breast milk]).

All infant growth velocity data will be listed.

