### 4.1.1 Inclusion Criteria

The following criteria must be met for study entry:

- An Informed Consent Form (ICF) for participation of the maternal subject and her infant (for collection of blood, infant demographic and adverse event data) is signed and dated by the subject. Where applicable, the written ICF with respect to the infant is also signed and dated by the holder of parental rights as designated by the maternal subject
- Woman is able and willing to comply with the study protocol, according to the judgment of the investigator, in particular:
  - Woman is willing to breastfeed (either exclusively, or with formula supplementation) for at least 60 days after the first postpartum ocrelizumab infusion (this decision is to be taken prior to and independent from study participation)
  - Woman is willing to provide breastmilk samples before and after their first and, if applicable, second postpartum ocrelizumab infusion
    - Note: Exposure to ocrelizumab includes administration of an initial split dose of two 300 mg infusions (in 250 mL 0.9% sodium chloride) separated by 14 days for women initiating treatment with ocrelizumab, or a single 600 mg infusion (in 500 mL 0.9% sodium chloride) for women already on treatment with ocrelizumab.
- Woman is between 18 and 40 years of age at screening
- Woman has a diagnosis of MS or CIS (in line with the locally approved indications)

- Woman has delivered a healthy term singleton infant (≥37 weeks gestation)
- Infant is between 2–24 weeks of age at the time of the mother's first postpartum dose of ocrelizumab
- For women who received commercial ocrelizumab (OCREVUS) before enrolment: documentation that last exposure ocrelizumab occurred more than 3 months before the LMP (i.e., excluded a potential fetal exposure) and was given at the approved dose of 2×300 mg or 1×600 mg
- Woman agrees to use acceptable contraceptive methods or alternative methods during the study as described below and, if applicable, upon study treatment discontinuation, as defined by the local prescribing information (see Section 4.6.1).

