### 4.5.3.2 Physical Examinations and Related Assessments

- Body weight (measured at every visit where a blood sample will be taken, i.e., at Day 30 [±2 days] post-infusion 1, and 1 month (+30 days) after the first or second dose of MMR vaccine or at Month 13 of age [+30 days] if MMR vaccine is not planned to be administered). Infant weight will be collected by a mobile nurse during home visits or by qualified site staff if the visit occurs at the site.
- Feeding schedule diary (during the treatment and sampling period): Women should record the number of breastmilk feeds and/or feed with formula milk (supplementation) on the day of the sample collection and the previous and following day, i.e., day of collection ±1 day. The mother's record of the feeding schedule diary will be collected by study personnel at the site or by a mobile nurse during visits to the mother.
- Feeding status (during the vaccination period): Women should record feeding status of the infant, i.e., whether exclusive breastfeeding, mixed feeding (partial breastfeeding along with infant formula and/or baby food), exclusive infant formula feeding, or fully weaned, at Months 2, 4, 6, 9, and 12, as applicable and depending on the infant's age at enrolment. The mother's record of feeding status will be collected by study personnel at the site or by a mobile nurse during visits to the mother.
- ASQ-3 at Months 2, 4, 6, 9, and 12, as applicable and depending on the infant's age at enrolment.
- Growth velocity (weight, length and head circumference), using growth charts according to the WHO Child Growth Standards (WHO 2022); as well as absolute values (other standard measurements recorded by e.g., the pediatrician as part of routine postnatal care may also be used) at Months 2, 4, 6, 9, and 12, as applicable and depending on the infant's age at enrolment.

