# Appendix 6 Time Windows for Infant Growth Velocity and Child Developmental Milestone Assessments

The following time windows must be applied for the assessment of growth velocity and child developmental milestones at Months 2, 4, 6, 9, and 12:

Timepoint	Associated time window
Month 2	1 month 0 days through 2 months 30 days
Month 4	3 months 0 days through 4 months 30 days
Month 6	5 months 0 days through 6 months 30 days
Month 9	9 months 0 days through 9 months 30 days
Month 12	11 months 0 days through 12 months 30 days

The following visualization depicts the timepoints and corresponding time windows based on the infant's month of age:

To calculate whether the infant falls under the respective assessment window based on its date of birth, the Ages and Stages Questionnaire, version 3 (ASQ-3) age calculator2 can be used: https://agesandstages.com/free-resources/asq-calculator/.

Assessment of growth velocity at Months 2, 4, 6, 9, and 12 (as applicable and depending on the infant's age at enrolment) must fall under the corresponding time windows of the ASQ-3; however, the date of assessment or data collection does not need to correspond to the same date of ASQ-3 assessment. Whenever possible, assessment of growth velocity may be collected as part of the infant's routine post-natal care visits performed by e.g., the pediatrician.

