### 6.4 SUMMARIES OF DEMOGRAPHIC AND BASELINE CHARACTERISTICS

For women, demographics (age and self-reported race), medical history, and neurological examination will be summarized. The following will also be summarized: MS disease history (duration since first MS symptoms, duration of MS since diagnosis, relapses in the past year), and other important variables.

Characteristics of infants at birth will also be summarized (gender, weight, gestational age at birth and other endpoints collected). Values at the mother's first ocrelizumab infusion visit (which may take place any time between Week 2 and Week 24 postpartum) will be considered as baseline.

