3.3 DATA MONITORING

There is no Independent Data Monitoring Committee (IDMC) planned for this study.

4. STATISTICAL METHODS

The analysis of this open-label study will be primarily based on descriptive statistical methods. Unless otherwise specified, statistical tests will be exploratory in nature. Corresponding 95% confidence interval (CI) will be presented as appropriate. No correction for multiple testing will be applied.

For continuous variables, descriptive statistics (e.g., number of patients [n], mean, standard deviation [SD], median, 25th and 75th percentiles, minimum, maximum) will be calculated and summarized.

For categorical variables, the number and percentage in each category will be displayed.

Unless specified otherwise, values at the mother's first ocrelizumab infusion visit (which may take place any time between Week 2 and Week 24 post-partum) will be considered as baseline for all analyses. For analyses in the infant, date of birth will be considered as baseline.

Note that the protocol's Schedule of Assessments (see Appendix 2) defines the day of first post-partum ocrelizumab administration as Day 0, whereas per the Clinical Data Interchange Standards Consortium (CDISC) standards the analysis defines it as Day 1, i.e., Study Day=Date of assessment – Day of first post-partum ocrelizumab dose + 1. Study day will be defined in the footnotes of outputs as appropriate. The primary analysis time point will be described as the "Day 30 Visit" to highlight that it refers to the visit label defined in the protocol rather than the derived study day for analysis, since in this case the derived Study Day=31.

The analyses outlined in this Statistical Analysis Plan (SAP) supersede those specified in the protocol.

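### Infant growth velocity is defined as the average rate since birth, which dilutes any change starting at the mother's first infusion, most strongly for infants who enter late

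*SAP*

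**What the plan says.** The growth bullet in SAP 4.6.1 opens with "Actual values and change from baseline (defined as at birth) for weight", goes on to "length/height, head circumference, and growth velocity (defined as the change", and completes the definition with "from baseline divided by the number of months since baseline". The list of time-points for this summary is birth and Months 2, 4, 6, 9 and 12. The opening text of SAP Section 4 sets the same anchor in general: "For analyses in the infant, date of birth will be considered as baseline".

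Protocol 4.1.1 fixes when the mother may first be treated: "Infant is between 2–24 weeks of age at the time of the mother's first postpartum dose of ocrelizumab". Protocol 4.5.3.2 schedules growth measurements "at Months 2, 4, 6, 9, and 12, as applicable and depending on the infant's age at enrolment", and Appendix 6 gives wide windows around those ages; the Month 12 window, for example, is "11 months 0 days through 12 months 30 days".

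Protocol 6.4 uses a different reference point. There, "Values at the mother's first ocrelizumab infusion visit" serve as baseline. SAP Section 5, which lists departures from the protocol, does not mention the difference.

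SAP 4.6.1 also plans WHO percentiles at each time-point, change from baseline in percentile, shift tables, plots of mean percentiles, and a growth chart for every infant. The only growth subgroup is type of feed. No velocity between visits, no velocity after infusion and no split by age at first infusion is planned.

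**The concern.** A quantity called velocity would normally describe how fast an infant is growing over a recent interval. Here it is cumulative gain divided by age, so every later value carries all earlier growth with it. What starts at 2 to 24 weeks of age is possible ocrelizumab exposure via milk. Time before that point cannot reflect the drug, yet it stays in the numerator and denominator at every later visit.

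Protocol 3.3 gives evaluation of potential adverse impact on the infants as the reason for following growth and development. If growth slowed after the first infusion, the velocity summary would understate the slowing, by an amount that depends on age at entry. Pooling all infants at a given month mixes values that are almost entirely post-infusion with values that are largely pre-infusion. The summary is also listed at birth, where both the change and the elapsed time are zero.

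**Working it through.** The plan states no figure for growth velocity, so there is nothing to reproduce first. The check is direct arithmetic.

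**Inputs**
- Age at first infusion, e: 2 to 24 weeks (Protocol 4.1.1). At 7/30.4375 months per week this is 0.46 to 5.52 months.
- Age at assessment, T: nominally 2, 4, 6, 9 and 12 months (Protocol 4.5.3.2; SAP 4.6.1).
- Slowdown after infusion, s: 30%. This is an assumption for illustration; the documents give no effect size.

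**Formulas**
- Pre-infusion share of the averaging period = min(1, e/T).
- With a constant rate r before e and r(1 − s) after it, the gain by T is re + r(1 − s)(T − e) = r[T − s(T − e)]. Dividing by T, the since-birth velocity is r[1 − s(T − e)/T], so the visible slowdown is s(T − e)/T.

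**Week 24 entry, e = 24 × 7/30.4375 = 5.52**
- Month 6: share 5.52/6 = 92%; visible slowdown 0.30 × 0.08 = 2%.
- Month 9: share 5.52/9 = 61%; visible slowdown 0.30 × 0.39 = 12%.
- Month 12: share 5.52/12 = 46%; visible slowdown 0.30 × 0.54 = 16%.
- Months 2 and 4: any value is wholly pre-infusion.

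**Pre-infusion share across the entry range**

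| Entry week | Month 6 | Month 9 | Month 12 |
|---|---|---|---|
| 2 | 7.7% | 5.1% | 3.8% |
| 13 | 49.8% | 33.2% | 24.9% |
| 20 | 76.7% | 51.1% | 38.3% |
| 24 | 92.0% | 61.3% | 46.0% |

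**When the share passes one half.** Setting e = T/2 and converting to weeks gives Week 4.3 for Month 2, 8.7 for Month 4, 13.0 for Month 6, 19.6 for Month 9 and 26.1 for Month 12. The last lies beyond the Week 24 entry limit. Across the Month 12 window, a Week 24 entrant runs from 5.52/11 = 50.2% to 5.52/13 = 42.5%.

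**Sensitivity to the shape of growth.** If cumulative gain is proportional to age to the power b, the pre-infusion share of the gain is (e/T)^b. For Week 24 entry at Month 12 this is 46% (b = 1), 56% (b = 0.75) or 68% (b = 0.5). These values of b are assumptions; the documents contain no growth curve.

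**Between-visit rates.** At nominal ages, the Month 6–9 and Month 9–12 intervals contain no pre-infusion time for any eligible infant, because e is at most 5.52. For Week 24 entry the Month 4–6 interval is (5.52 − 4)/2 = 76% pre-infusion and has to be treated as straddling. Actual ages matter: the Month 6 window in Appendix 6 opens at 5 months 0 days, so for a late entrant a Month 6 value may precede the infusion.

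**The case against.** The stated exploratory objective is growth in the first year of life, and a since-birth rate fits that wording. The study is single-arm and descriptive, with no planned before/after contrast. Birth is also the one scheduled anchor available for every infant: the Schedule of Assessments has no infant weight, length or head circumference at Day 0. A reader might infer from Protocol 6.4 that the SAP wrongly moved the baseline. The documents do not support that. The sentence sits in the section on baseline characteristics, Protocol 6.5.3 defers exploratory derivations to the SAP, and a Day 0 anchor could not be computed from scheduled data. Birth as baseline is defensible.

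The other displays also matter. Visit-specific percentiles, mean-percentile plots and individual WHO charts are not averaged since birth, and a slowdown could show there. A reader who inferred that the plan cannot reveal one would be wrong. This protection is partial, because change-from-baseline percentiles and the shift tables are anchored at birth too. The shift tables have a single top category above the 50th percentile, so a fall from the 95th to the 55th would not register.

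Interval velocity has limits of its own. Month 2 and Month 4 values are collected only as the age at enrolment allows. If a Week 24 entrant has neither, the last earlier value is birth, and the Month 6 interval rate equals the SAP's value.

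What stands after all this is that the summary labelled velocity dilutes an effect starting at infusion, and that nothing separates infants by age at first infusion.

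**Conclusion.** The point holds as a minor improvement to an exploratory, descriptive endpoint. Under constant growth, a change starting at first infusion is attenuated by (T − e)/T. The retained fraction for Week 24 entry is 8%, 39% and 54% at Months 6, 9 and 12; for Week 2 entry it is about 96% at Month 12.

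Two stronger readings should be resisted. A reader might infer that most of a late entrant's velocity predates exposure at every visit. By time, that is true at Month 6 only for entry after about Week 13, at Month 9 only after about Week 20, and never at nominal Month 12. A reader might also infer that true dilution is larger because infants grow faster early on. That is possible, but the documents give no growth curve, so the 46% to 68% range above is illustration only.

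The result rests on nominal ages, constant growth and an effect that begins at the infusion date. The 30% slowdown is an assumption; the attenuation factor does not depend on it.

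**What to change.** In SAP 4.6.1:
- Define growth velocity as the change between consecutive available assessments divided by the actual months between them.
- Flag each interval as pre-infusion, straddling or post-infusion from the date of first infusion, and summarise post-infusion intervals separately.
- Keep change from birth as a descriptive row, and drop velocity at birth.
- Optionally, add change in WHO percentile or z-score from the last pre-infusion measurement, noting that this may be birth for late entrants.

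This needs SAP wording and programming only, and uses measurements already planned. The price is noisier values over shorter intervals. Early intervals may be missing for late entrants, for whom the first usable post-infusion interval may be Month 6–9.

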2. STUDY DESIGN

This is a prospective, multicenter, open-label study in lactating women with clinically isolated syndrome (CIS) or MS (in line with the locally approved indications) who decided together with their treating physician to continue on, or start treatment with, OCREVUS® (ocrelizumab) post-partum despite ocrelizumab currently not being recommended during lactation.

This study will enroll at least 10 women with CIS or MS who are breastfeeding or planning to breastfeed. Laboratory and clinical assessments will be performed as described in the Schedule of Assessments presented in Appendix 2.

The study will consist of the following periods:

- Screening period
- Treatment and sampling period
- Vaccination period

Figure 1 presents an overview of the study design. The schedule of assessments is provided in Appendix 2.

n=20 women/infants Treatment and sampling period Vaccination period Week Week Birth ~Month 13 Infant age 2-24 6-28 (1 month post-MMR) Day Day 14* 15* Day 30 (± 2 days) Day 60 (± 2 days) Day Day Study visit OCR infusion Co-Primary Endpoint Milk sample ocrelizumab via breastmill **Blood sample** 0 (mother & infant) Clinical visits Questionnaires & Growth Charts

Figure 1 Overview of Study Design

Samples and visits at Days 14, 15 and 21 apply only to patients initiating treatment with ocrelizumab at 2×300 mg separated by a 14-day interval.

ASQ-3=Ages and Stages Questionnaire, version 3; CIS=Clinically isolated syndrome; LMP=last menstrual period; MS=Multiple Sclerosis; OCR=Ocrelizumab.

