2.2 DETERMINATION OF SAMPLE SIZE

There is no formal sample size calculation, as no confirmatory hypothesis testing is planned. The primary analysis will be descriptive. The study will include at least 10 women with CIS or MS (in line with the locally approved indications) who are breastfeeding or planning to breastfeed.

With 10 infants, a precision (width of the two-sided 95% CI) of 0.443 is expected if one event is observed (defined as B cells below the lower limit of normal [LLN]) and a precision of 0.531 if two events are observed in the study. If no event is observed during the study, there is a 95% confidence that the event rate is below 0.31.

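### SAP 4.6.1 averages infant growth on the WHO percentile scale, so the group summaries respond least in the smallest infants; z-scores should be added, and the 90% interval aligned or justified

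*SAP*

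**What the plan says.** SAP 4.6.1 takes birth as baseline and reports growth at Months 2, 4, 6, 9 and 12 in the infant safety set. On the age-adjusted scale, for weight, length/height and head circumference, it states that "change from baseline percentiles at each time-point will be summarized", and "Mean percentiles for weight-for age, length/height-for-age, and head circumference-for-age and corresponding 90% CIs will be plotted over time". Z-scores are not mentioned.

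The same section also plans actual values, change from birth and velocity in kg and cm; counts by percentile class and within the 3rd–97th and 10th–90th; shift tables whose end classes are 3rd or below and above the 50th; a WHO chart for each infant with the 3rd percentile as its lowest reference line; combined trajectory plots by sex; and a full listing.

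On interval level, SAP Section 4 says "Corresponding 95% confidence interval (CI) will be presented as appropriate". Protocol Section 6 also sets 95%. Protocol Section 6.5.2 gives monthly infant length and weight as its example of continuous variables, and it ends by promising means with 95% CIs for continuous variables. SAP Section 5, which lists departures from the protocol, contains one item (the name of the mothers' pharmacokinetic set) and does not mention growth.

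**The concern.** A percentile is a rank and a z-score is a distance. Averaging ranks gives the same biological loss a different weight according to where the infant starts, with the least weight at the bottom of the chart. The mean percentile and its change are the only age-adjusted continuous group summaries of growth in the plan.

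The raw kg and cm summaries cannot stand in for them. They carry no age or sex reference, and Protocol Appendix 6 allows the Month 2 assessment anywhere from 1 month 0 days to 2 months 30 days. Velocity divides by months elapsed, but it is still not set against a reference. The group estimate reported for this endpoint could therefore look flat although small infants had lost ground.

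The 90% level is a separate matter: one figure uses a narrower interval than the rest of the plan, and no reason is given.

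**Working it through.** **The plan's own figures.** The SAP gives no numerical figure for growth. Its only precision figures are for the B-cell proportion with 10 infants: "With 10 infants, a precision (width of the two-sided 95% CI) of 0.443 is expected if one event is observed". Exact Clopper-Pearson limits reproduce them:
- 1/10 gives 0.0025 to 0.4450, width 0.4425 (stated 0.443).
- 2/10 gives 0.0252 to 0.5561, width 0.5309 (stated 0.531).
- 0/10 gives an upper limit of 0.3085 (stated 0.31).

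n=10 is used below because SAP Section 2 plans at least 10 pairs.

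**Compression.** Percentile = 100·Φ(z). Points lost for a fall of d SD from percentile p are p − 100·Φ(z_p − d). Compression is the points lost from the 50th divided by the points lost from p. The size of fall and the starting percentiles are assumptions, because the documents give none. With d = 1:

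| Start | Points lost | Compression against the 50th |
|---|---|---|
| 50th | 50 − 15.87 = 34.13 | 1 |
| 25th | 20.30 | 34.13/20.30 = 1.7 |
| 10th | 8.87 | 34.13/8.87 = 3.8 |
| 5th | 4.59 | 34.13/4.59 = 7.4 |
| 3rd | 2.80 | 34.13/2.80 = 12.2 |
| 2.3rd | 2.14 | 34.13/2.14 = 16.0 |

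From the 3rd, a fall of 0.5 SD gives 9.0-fold and a fall of 2 SD gives 15.9-fold. On the z scale every 1 SD fall counts as 1.00, so the ratio is 1 throughout.

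**Effect on a group mean.** Take 10 infants evenly spread at the 5th, 15th, …, 95th percentiles, with mean 50.0.
- The two smallest each fall 1 SD: (4.59 + 12.91)/10 = 1.75 points, so the mean goes to 48.2.
- The two in the middle (45th and 55th) each fall 1 SD: the mean goes to 43.2, a drop of 6.8 points.
- In both cases mean z falls by 2 × 1/10 = 0.20.

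The same growth loss therefore moves the planned summary almost four times as far in one case as in the other (6.8/1.75 = 3.9).

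**Shift classes.** An infant already at or below the 3rd who falls further stays in the lowest class. An infant who falls from the 97th (z = 1.88) to the 51st (z = 0.03), about 1.86 SD, stays in the top class. In the count within the 10th–90th, that second infant moves into range.

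**Interval level.** The SAP names no method for this plot, so a t-interval is assumed. With 9 df the quantiles are 1.833 (90%) and 2.262 (95%). 1.833/2.262 = 0.81, so the 90% interval is 19% narrower; conversely 2.262/1.833 = 1.23. With evenly spread percentiles (SD 100/√12 = 28.9), the half-width is 1.833 × 28.9/√10 = ±16.7 points at 90% and ±20.7 at 95%. For z with SD 1, it is ±0.58 and ±0.72.

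**The case against.** The strongest reply is that the plan does not depend on the mean-percentile plot. With about 10 infants every curve can be read directly, and the individual charts, trajectory plots, counts at the 3rd percentile, raw values and listings would show an infant who falters. Percentiles are how WHO charts are read, and the protocol endpoint asks for those charts plus absolute values. The endpoint is exploratory and nothing is tested: "There is no formal sample size calculation, as no confirmatory hypothesis testing is planned". A mean z-score dilutes too: in the example above, two infants falling 1 SD moved it by only 0.20.

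Most of this stands, and it rules out several stronger readings that a reader might draw:
- **That growth faltering could go unseen.** This is true only of the group percentile summaries; the individual-level displays would show it.
- **That falls in small infants are compressed twelve-fold in general.** That is one case, a 1 SD fall from the 3rd against the 50th. The range is about 4-fold at the 10th to 16-fold at the 2.3rd. Because Protocol 4.1.1 admits only healthy singletons born at term, starts near the 3rd should be uncommon, although no birth-weight limit is set.
- **That growth is the plan's check for harm to infants.** Adverse events, B-cell counts, infant serum concentration, vaccine responses and ASQ-3 are all planned as well.
- **That the plotted intervals would leave the 0–100 range.** With a mean near 50 and a half-width near 17, this is unlikely.
- **That 95% intervals would help to reveal faltering.** They are wider and would not.

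What the reply does not supply is a group estimate of age-adjusted change that treats equal losses equally. Charts and listings are not group estimates, the raw summaries are not age-referenced, and neither the shift classes nor the chart reference lines grade falls below the 3rd. On the interval level, SAP Section 4 does say that its analyses supersede the protocol's, but the departure is neither explained nor listed in Section 5.

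**Conclusion.** The point holds as a minor one, confined to the group summaries of an exploratory endpoint. Mean percentile and mean percentile change weight a 1 SD fall at 34 points from the 50th, 8.9 from the 10th and 2.8 from the 3rd, so they are least responsive in the smallest infants. The shift tables do not fill that gap in their end classes. The 90% level is an unexplained inconsistency with SAP Section 4 and Protocol Sections 6 and 6.5.2; under a t-interval at n=10 it makes the plotted interval 19% narrower than a 95% one. No error rate, sample size or decision rule is affected.

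The compression figures rest on converting between percentile and z by the normal distribution and on the assumed falls and starting points. The ten-infant example also assumes evenly spread percentiles.

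**What to change.** In SAP 4.6.1, add weight-for-age, length/height-for-age and head-circumference-for-age z-scores from the WHO standards already cited in SAP Section 6. Summarise the mean and the change from birth at each time point with 95% CIs, and plot mean z over time. Keep the percentile categories, shift tables and individual charts as descriptive displays.

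As a separate consistency correction, use 95% for the growth plot, or list the 90% level in SAP Section 5 with a reason.

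The cost is a few lines of SAP text and minor programming. No new data are needed. The plotted intervals become 1.23 times as wide at n=10.
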